### 3.2. Hypotheses related to test findings

#### 3.2.1. Gastric emptying of solids and liquids

Patients will undergo a gastric emptying scintigraphy test that simultaneously measures gastric emptying of solids and liquids for their clinical evaluation.

- Delayed gastric emptying is linked to greater impairment in quality of life, increased economic cost, increased healthcare utilization, and worse clinical outcomes.
- Profound delays in solid food gastric emptying (e.g. less than 10% emptied at 2 hours or less than 25% emptied at 4 hours) relate to symptoms, whereas mild delays (e.g. 25- 50% emptied at 2 hours or 50-90% emptied at 4 hours) have little correlation with symptoms.
- Patients with nausea and vomiting and normal gastric emptying can be distinguished from slow emptyers based on clinical history.
- Gastric emptying improves over time in a subset of patients with gastroparesis. Conversely, patients with symptoms but normal gastric emptying at presentation may manifest delayed emptying if retested within a year.
- Gastric emptying can be variable on repeat testing in patients with gastroparesis symptoms. Specifically, some patients with normal gastric emptying initially but with symptoms of gastroparesis may develop delayed gastric emptying on repeat testing. On the other hand, patients with delayed gastric emptying will continue to have delayed gastric emptying.
- Gastric emptying of liquids identifies additional patients with gastroparesis who have normal gastric emptying of solids.
- Gastroparetic symptoms correlate better with gastric emptying of solids than to gastric emptying of liquids.
- Patients with delayed gastric emptying of both solids and liquids have more severe symptoms, and worse quality of life than patients with normal gastric emptying or isolated delay in either gastric emptying of solids or liquids.

#### 3.2.2. Regional gastric emptying

Images from each gastric emptying scintigraphy test will be saved to assess emptying from the proximal and distal regions of the stomach.

- Regional gastric emptying with analysis of proximal and distal emptying improves the identification of gastric transit abnormalities over the conventional analysis of only total gastric emptying.
- Delayed gastric emptying from the proximal stomach is associated with early satiety and postprandial fullness. Delayed gastric emptying from the distal stomach is associated with symptoms of nausea and vomiting.

### 3.2.3. Wireless motility capsule

- Wireless motility capsule (WMC) studies will reveal a subset of patients with gastroparesis who also have subtle or overt dysmotility of the small and/or large intestine which will adversely impact prognosis.
- WMC methods detect delays in gastric emptying in higher percentages of patients with suspected gastroparesis versus 4 hour gastric retention on scintigraphy. **Expectation:** We anticipate WMC will show delays in 60% of patients with symptoms suggestive of gastroparesis vs. in 40% with gastric scintigraphy based on data from initial trial of WMC in patients with prior scintigraphic demonstration of gastroparesis.
- Delays in small intestinal and/or colon transit are frequently observed in patients with symptoms suggestive of gastroparesis. **Expectation:** We anticipate WMC methods will detect delays in small intestinal transit in 20% and delays in colon transit in 50% of patients with suspected gastroparesis. Generalized transit delays in 2 or 3 regions (stomach, small intestine, colon) will be observed in 35% of patients with suspected gastroparesis based on data from prior published retrospective analysis of UMI and MGH databases.
- Different symptom profiles correlate with distinct gastric and extragastric motor defects.

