#### Inclusion criteria

- Symptoms of gastroparesis of at least 12 weeks duration with varying degrees of nausea, vomiting, early satiety, postprandial fullness, and/or abdominal pain
- An etiology of either diabetic, idiopathic, or post-Nissen fundoplication gastroparesis
- Gastric emptying scintigraphy of solids and liquids using the 4 hour Egg Beaters® protocol within the last 6 months with either:
  - Abnormal gastric emptying rate defined as an abnormal 2 hour (>60% retention) and/or 4 hour (>10% retention) result based on a 4-hour scintigraphic low fat Egg Beaters® gastric emptying study performed at a GpCRC clinical center. (This group will comprise ~80% of patients in the registry.)
  - Patients with a normal gastric emptying rate, but who have symptoms of gastroparesis. (This group will comprise ~20% of patients in the registry.)
- Age at least 18 years at initial screening visit

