#### **Subhypotheses:**

- a. Fullness and early satiety severity correlates with delays in gastric emptying. **Expectations:** Postprandial fullness/early satiety subscale scores on the Gastroparesis Cardinal Symptom Index (GCSI) show progressive increases from normal WMC gastric emptying (<5 hr) to mildly delayed WMC gastric emptying (5-12 hr) to severely delayed WMC gastric emptying.
- b. Bloating and distention severity correlates with delays in small intestinal and colonic transit. **Expectations:** Bloating/visible distention subscale scores on the GCSI are greater in those with small bowel (SB) transit > 6 hr versus those with SB transit < 6 hr. Bloating/visible distention subscale scores also show progressive increases from normal WMC colon transit (<59 hr) to moderately delayed WMC colon transit (59-100 hr) to severely delayed WMC colon transit (>100 hr).
- c. Upper abdominal pain and discomfort correlate with abnormalities in pressure profiles in the stomach or small intestine. **Expectations:** Upper abdominal pain/discomfort subscale scores on the GCSI are greater in those with gastric contractions >29 and motility indices (MI) >9.82 in the hour before gastric emptying vs. in those with lower values. Upper abdominal pain/discomfort subscale scores are greater in those with elevated SB contractions and MI vs. in those with lower values.
- d. Symptom onset after meal ingestion and duration will correlate with the region of motor impairment. **Expectation:** Postprandial fullness/early satiety and upper abdominal pain/discomfort scores on visual analog scale (VAS) testing will begin earlier and resolve quicker as they derive predominantly from gastric dysfunction, whereas bloating and distention will peak later and persist longer due to their genesis in the small intestine and/or colon.

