#### **4.3 Target composition**

Patients will be recruited predominantly from outpatient clinics either in gastroenterology, diabetes, or primary care settings. Inpatients (patients in the hospital) with the diagnosis of gastroparesis will also be invited to participate.

In GpR 2, we will cap the number of the patients with symptomatic nausea and vomiting with normal gastric emptying (as described in section 4.2 above) to 20% of the total patients enrolled. In the GpR 2, patients with prior Nissen fundoplication will be eligible for enrollment and we will cap the patients with post-Nissen gastroparesis to 20% of the patients with delayed gastric emptying. Assuming the goal of 500 patients are entered into GpR 2 and assuming similar types of enrollment as in the first registry this will result in the following types of patients: 200 idiopathic gastroparesis patients, 50 idiopathic patients with normal gastric emptying, 120 with diabetic gastroparesis, 30 diabetic patients with normal gastric emptying, 80 post-Nissen gastroparesis patients, and 20 post-Nissen patients with normal gastric emptying.

---

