#### *SmartPill® transit and contractile parameters collected*

Gastric emptying will be calculated from time of ingestion to the time the capsule passes to the duodenum as defined by abrupt  $>2$  pH unit increases from the lowest postprandial value to  $>4$  that do not decrease to  $<4$  for  $>10$  minutes. Gastric emptying  $>5$  hr is considered delayed. Ileocecal passage

is defined when >1 pH unit decreases occur >30 min after gastric emptying; such pH decreases are noted in >95% of cases. Small bowel transit will be calculated from times of duodenal to ileocecal passage. Small bowel transit >6 hours is considered delayed. Anal expulsion is determined by 0.045°F/second temperature decreases. Colon transit will be calculated from times of ileocecal passage to anal expulsion. Colon transit >59 hours is considered delayed. Two pressure parameters will be computer calculated (MotilitGI, GIMS Data Viewer, SmartPill Corp., Buffalo, NY). Numbers of contractions >25 mmHg will be standardized to activity per 15 min to compare gastric, small bowel, and colon recordings of different length. Summed contractility measures >25 mmHg per 15 minutes will be provided by motility indices calculated as log (mmHg x min). Numbers of gastric contractions <29 and motility indices <9.82 in the hour before gastric emptying are considered abnormal.

Symptom profiles in those with isolated delayed gastric, small bowel, and colon transit as well as with generalized transit delays in >2 gut regions, and normal transit throughout. Symptoms will be compared in those with increased vs. normal vs. decreased contractile parameters in the same subsets. These studies will provide detailed characterizations of diffuse and generalized gut transit and contractile abnormalities in patients presenting with symptoms of gastroparesis.

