#### 6.7.6. Standardized questionnaires

Several standardized questionnaires will be administered at baseline (prior to enrollment) and during follow-up at specified intervals (see Appendix [11.2](#) for the data collection schedule). The purpose of the questionnaires is to obtain important information regarding gastroparesis symptoms, nutrition, pain, and health-related quality of life.

**Patient Assessment of Upper Gastrointestinal Disorders-Symptoms (PAGI-SYM).** The self-reported questionnaire is composed of 20 items and 6 subscales. The severity of each symptom item over a 2-week recall period is scored from 0 (none or absent) to 5 (very severe). The GCSI, a 9 symptom survey relevant to gastroparesis stratified in 3 subscales—nausea/vomiting, fullness/early satiety, and bloating, is contained in the PAGI-SYM. The GCSI correlates with patient severity ratings and is responsive to changes in overall symptoms. Two additional items for constipation and diarrhea also will be recorded and scored and their main symptom will be determined.

**Patient Assessment of Upper Gastrointestinal Disorders-Quality of Life (PAGI-QoL).** A validated 30 item questionnaire to assess quality of life in patients with dyspepsia, GERD, or gastroparesis. Copyright© 2004 Johnson & Johnson.

**Rome III Diagnostic Questionnaire for Adult Functional GI Disorders.** The Rome Foundation has developed a 93 item diagnostic questionnaire to assist physicians, health care professionals and researchers in identifying individuals who have one or more functional gastrointestinal disorders (FGIDs). Rome III modules for (1) nausea, vomiting, and belching and (2) functional dyspepsia to assess upper symptoms and (3) functional bowel disorders to assess lower symptoms are validated surveys from the Rome Foundation to quantify symptoms and suggest functional disorders involving the upper or lower gut. Copyright© 2006 by Douglas A. Drossman, Enrico Corazzari, Michel Delvaux, Robin C. Spiller, Nicholas J. Talley, W. Grant Thompson, William E. Whitehead.

**Beck Depression Inventory, Second Edition (BDI-II).** The BDI-II is a commonly used, reliable 21-item self-report measure designed to assess for depression.

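### The capsule-versus-scintigraphy detection hypothesis (60% vs 40%) cannot be validly tested on overall rates, because the scan that qualifies patients for enrolment is also the comparator

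*Protocol*

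**What the plan says.** Section 3.2.3 states the hypothesis: "WMC methods detect delays in gastric emptying in higher percentages of patients with suspected gastroparesis versus 4 hour gastric retention on scintigraphy". It then gives the expected size: "We anticipate WMC will show delays in 60% of patients with symptoms suggestive of gastroparesis vs. in 40% with gastric scintigraphy". The source of those figures is named as well: "based on data from initial trial of WMC in patients with prior scintigraphic demonstration of gastroparesis".

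Enrolment is sorted on baseline scintigraphy. The criterion for delay (Design synopsis and section 5.1) is more than 60% retained at 2 hours, more than 10% at 4 hours, or both. Of the delayed patients the synopsis says: "This group will comprise ~80% of patients in the registry". Section 4.3 caps patients with normal emptying "to 20% of the total patients enrolled". Section 7 and Table 5 plan 400 delayed and 100 not delayed, and the Table 6 footnote gives that split for the 4-hour baseline scan. The capsule is given at baseline only.

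Subhypothesis c in section 3.2.3 ties upper abdominal pain to abnormal pressure profiles and expects that pain scores "are greater in those with gastric contractions >29 and motility indices (MI) >9.82 in the hour before gastric emptying". Section 6.7.3 says: "Numbers of gastric contractions <29 and motility indices <9.82 in the hour before gastric emptying are considered abnormal". Subhypothesis c takes the pain score from a GCSI subscale, but section 6.7.6 describes the GCSI as "a 9 symptom survey relevant to gastroparesis stratified in 3 subscales": nausea/vomiting, fullness/early satiety and bloating.

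**The concern.** Comparing the overall positivity of two tests is informative only if neither test decided who is in the sample. Here one of them did. The share positive on scintigraphy follows from the enrolment cap, while the share positive on the capsule is free to vary. The difference then mostly measures the cap.

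At stake is a diagnostic conclusion. An analyst who follows the hypothesis as worded would probably report that scintigraphy detects more delay than the capsule, and an enrolment artefact would be read as a property of the tests. Section 7 reserves the exploratory label for hypotheses that were not pre-specified, so this one would not carry that caution.

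**Working it through.** **Inputs.** Composition from section 4.3; expected rates from section 3.2.3; capsule sensitivity 65% and specificity 87% from section 6.7.3; first-registry 4-hour retention (mean 25.1, SD 23.4) from Table 6.

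**1. Reproduce the planned mix.** Delayed: 200 + 120 + 80 = 400. Normal: 50 + 30 + 20 = 100. 400/500 = 80%. This agrees with Table 5 and the synopsis.

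**2. The contrast at the protocol's own capsule rate.** 60% - 80% = -20 points, against +20 expected. With 500 paired results, let b be the share delayed on the capsule only and c the share delayed on scintigraphy only, so b - c = -0.20. McNemar z = (b - c)√500 / √(b + c).
- b = 0, c = 0.20: z = -10.0.
- b = 0.20 (all scintigraphy-normal patients capsule-delayed), c = 0.40: z = -5.8.

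**3. When could the capsule lead?** Let s and f be the capsule-delayed shares among scintigraphy-delayed and scintigraphy-normal patients. The capsule share is 0.8s + 0.2f. It exceeds 0.8 only if s > 1 - 0.25f.

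| f | s must exceed |
|---|---|
| 100% | 75% |
| 60% | 85% |
| 40% | 90% |

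**4. Illustration with s = 65%.** This is an assumption: the stated sensitivity was measured against a prior diagnosis, not a concurrent scan. The capsule share is 0.52 + 0.2f.
- f = 13% (1 minus the specificity in controls): 54.6%.
- f = 40%: 60%.
- f = 100%: 72%.

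All are below 80%.

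**5. Same tests, different selection.** Suppose 60% and 40% hold exactly in a sample where scintigraphy played no part in selection: 0.4s + 0.6f = 0.6, so f = 1 - 0.667s. With the same s and f in the registry, the capsule share is 0.8s + 0.2f = 0.667s + 0.2, and the difference is 0.667s - 0.6. It is positive only if s > 90%. At s = 65%, f is 56.7% and the result is 63% against 80%: +20 becomes -17 points with nothing changed but the selection.

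**6. Could 40% arise at 4 hours alone?** It would need 0.40 × 500 = 200 patients delayed at 4 hours, so 200 of the 400 enrolled as delayed would have to be delayed at 2 hours only. The Table 6 footnote says 400. As a rough check on the first registry's patients, a beta, gamma, normal or lognormal shape with the Table 6 mean and SD puts about 64% to 78% above 10% retention.

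**7. Sample size is not the obstacle.** Without selection, 60% vs 40% at 80% power and two-sided 0.05 needs 97 per group unpaired. Paired, n = (1.96√ψ + 0.84√(ψ - 0.04))² / 0.04, which gives 37 to 194 pairs for a discordant share ψ of 20% to 100%.

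**The case against.** The best reply has four parts.

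- **The quota and the comparator differ.** Enrolment uses 2 hours, 4 hours or both; the hypothesis names 4 hours. Patients delayed only at 2 hours count towards the 80% but are negative on the comparator. The Table 7 footnote defines the delayed group by either time point, so the 4-hour wording under Table 6 may be loose. Section 6.2 also lets patients who cannot swallow the capsule enrol, so the capsule-tested subset need not be 80/20. This stands as a limit on precision. If 64% were delayed at 4 hours and s = 65%, the capsule would lead once 0.52 + 0.2f > 0.64, that is f > 60%. The bias shrinks but remains.
- **The result is not predetermined.** A reader might infer that scintigraphy must come out ahead whatever the truth. The break-even in step 3 shows otherwise: the capsule can lead if agreement among delayed patients is very high.
- **The source was also a selected group.** A reader might infer that 60% vs 40% presumes unselected patients. Section 3.2.3 says the figures come from patients already diagnosed by scintigraphy. Section 6.7.3 gives 44% sensitivity for 4-hour scintigraphy in that work, which suggests a scan separate from the qualifying one. In this registry the qualifying scan is itself the comparator.
- **The consequence is limited.** This is one of many registry hypotheses, no sample size rests on it, and each analysis needs an approved proposal with its own statistical plan. That is true, but approval cannot undo selection in the data, and the protocol describes no unselected sample or reweighting.

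On subhypothesis c, a reader might infer that patients with normal contractility are placed in an abnormal group. The text labels no such group. It contrasts higher with lower values, and section 6.7.3 also plans a comparison of increased, normal and decreased contractility. What remains is a wording conflict and a misnamed subscale.

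**Conclusion.** The concern holds for the comparison of overall detection rates. The scintigraphy rate is set largely by enrolment, at about 80% by the enrolment criterion and possibly somewhat lower at 4 hours alone, so the expected 40% is not plausible. The bias runs strongly against the capsule: about -20 points at the protocol's own 60%, and reversal of a true +20 unless s exceeds 90% in the scenario of step 5. These sizes assume that the capsule-tested patients keep the 80/20 mix; step 4 also assumes s = 65%.

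It would go too far to say that the question is untestable in every form. Capsule results within each scintigraphy stratum remain estimable. The problem belongs to this hypothesis and not to the registry as a whole. The two inconsistencies in subhypothesis c are minor.

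**What to change.** In section 3.2.3, replace the overall comparison with two conditional estimates, each with a confidence interval:
- the share capsule-delayed among scintigraphy-normal patients;
- the share capsule-normal among scintigraphy-delayed patients.

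Give both with scintigraphic delay defined at 4 hours and by the enrolment criterion. Show the number delayed only at 2 hours, since these patients change group between the two definitions. State that overall detection rates are not comparable in this quota-sampled cohort.

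If all planned patients have a capsule result, the widest 95% half-widths are 1.96√(0.25/100) = 9.8 points for the 100 normal patients and 1.96√(0.25/400) = 4.9 points for the 400 delayed.

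In subhypothesis c, reconcile the reference to abnormal pressure profiles and the cut-offs above 29 and 9.82 with section 6.7.3, and name the PAGI-SYM upper abdominal pain subscale instead of a GCSI subscale.

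The cost is rewording, with no new data. The downside is that the overall detection claim is given up.

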#### **Subhypotheses:**

- a. Fullness and early satiety severity correlates with delays in gastric emptying. **Expectations:** Postprandial fullness/early satiety subscale scores on the Gastroparesis Cardinal Symptom Index (GCSI) show progressive increases from normal WMC gastric emptying (<5 hr) to mildly delayed WMC gastric emptying (5-12 hr) to severely delayed WMC gastric emptying.
- b. Bloating and distention severity correlates with delays in small intestinal and colonic transit. **Expectations:** Bloating/visible distention subscale scores on the GCSI are greater in those with small bowel (SB) transit > 6 hr versus those with SB transit < 6 hr. Bloating/visible distention subscale scores also show progressive increases from normal WMC colon transit (<59 hr) to moderately delayed WMC colon transit (59-100 hr) to severely delayed WMC colon transit (>100 hr).
- c. Upper abdominal pain and discomfort correlate with abnormalities in pressure profiles in the stomach or small intestine. **Expectations:** Upper abdominal pain/discomfort subscale scores on the GCSI are greater in those with gastric contractions >29 and motility indices (MI) >9.82 in the hour before gastric emptying vs. in those with lower values. Upper abdominal pain/discomfort subscale scores are greater in those with elevated SB contractions and MI vs. in those with lower values.
- d. Symptom onset after meal ingestion and duration will correlate with the region of motor impairment. **Expectation:** Postprandial fullness/early satiety and upper abdominal pain/discomfort scores on visual analog scale (VAS) testing will begin earlier and resolve quicker as they derive predominantly from gastric dysfunction, whereas bloating and distention will peak later and persist longer due to their genesis in the small intestine and/or colon.

### 3.2.4. Autonomic function testing

- Autonomic dysfunction is common among patients with gastroparesis, including those with idiopathic gastroparesis.
- Patients with increasing autonomic dysfunction have more severe symptoms and impairment in quality of life.
- Autonomic dysfunction is more common among patients with acute onset or post-infectious gastroparesis compared to patients with an insidious onset of gastroparesis.

- Patients with autonomic dysfunction have a more diffuse dysmotility compared to patients without autonomic dysfunction.
- Associated phenomena such as autonomic neuropathy or dysmotility of other gastrointestinal regions are important in determining the natural history and clinical outcomes in patients with gastroparesis.

#### **3.2.5. Electrogastrography**

- Ingestion of a standard solid meal evokes gastric dysrhythmias and upper GI symptoms that vary across a sub group of patients with gastroparesis.
  - Upper GI symptoms and gastric dysrhythmias are evoked by the water load satiety test in the majority of patients with idiopathic and diabetic gastroparesis.
  - Frequency of normal 3 cycles per minute (cpm) activity will vary across subgroups of patients, based on demographics, clinical and gastric pathophysiological characteristics compared with patients with gastric dysrhythmias.
  - Selected characteristics of the EGG signal and volumes of water ingested correlate with gastric emptying rates and upper GI symptoms and may predict emptying abnormalities.
  - Satiety meal testing at baseline correlates with baseline symptoms of severity as well as outcome after 1 or more years but not with gastric emptying.
-

## 4. Case definitions for Gastroparesis Registry 2

---

